4. SELECTION AND ENROLLMENT OF PARTICIPANTS

Subjects for these experiments over 5 years will include: Forty women with premenstrual dysphoric disorder (PMDD). As only women have menstrual cycles, only women will be sought. As women generally do not develop significant premenstrual mood symptoms until late adolescence, and the menstrual cycle may become irregular during the perimenopause, only women age 18-45 years will be studied. For these reasons, children and adolescents under the age of 18 and peri- and post-menopausal women will be excluded. All ethnic groups will be represented (Caucasian, Asian, Black, Hispanic and Other). We will focus on recruiting subjects representative of the community: approximately 54% Caucasian, 30% Hispanic, 10% Asian, 5% African American and 1% Other. The UCSD Medical Center serves a clientele in which minorities are over-represented. All subjects will be adults individually competent to execute written informed consent.

Recruitment of minority subjects: We will take pains to recruit women of color and other minorities working with the Women’s Center, the Cross Cultural center, the Lesbian, Gay, Bi-Sexual and Transgender (LGBT) Resource Center, Queer People of Color (QPOC) Center and the Native American Student Alliance on the University of California campus.

	Caucasian	Hispanic	Asian	Black	Other
Female	54%	30%	10%	5%	1%

4.1 Inclusion Criteria

PMDD women wishing to participate in this study must meet the following inclusion criteria:

- Age: 18-45 years.
- Women with regular ovulatory menstrual cycles 26-32 days in length (for at least the previous six months).
- A history of a depressive (but not bipolar) mood disorder, but not an ongoing episode (symptom free for the last 12 months).
- Patients must meet DSM-IV criteria for Premenstrual Dysphoric Disorder (that includes irritability).
- Objective ratings: mean of HRSD total scores across evaluation weeks 1-8 \leq 7 for follicular phase (day 5-10 of cycle after menses); mean of total HRSD

scores across evaluation weeks 1-8 ≥ 14 for premenstrual (luteal) phase (6 days prior to onset of menses onward).

- Subjective ratings: mean of Beck Depression Inventory total scores across evaluation weeks 1-8 < 10 follicular phase; ≥ 10 premenstrual (luteal) phase.
- Daily ratings: minimal symptoms (mean less than 50 on 100mm scale) follicular phase; at least a 30% increase in mean affective symptom ratings, premenstrual (luteal) phase.
- By clinical assessment and ratings, the patient has reported a history (for at least the last six months) of recurrent, moderate to severe premenstrual mood symptoms that impair some aspect of social or occupational functioning and that remit within a few days after the onset of menses. This pattern is prospectively documented with subjective daily mood ratings (DMR – visual analogue scale) during at least two consecutive symptomatic cycles. Symptom severity will also be documented with objective and subjective ratings over that time. Patients must demonstrate a consistency of symptoms and a long enough duration of symptoms (7-10 days) to allow for study.
- Subjects willing to endure the rigors of a long-term (up to 6 months) research study.

4.2 Exclusion Criteria

Participants meeting any of the following exclusion criteria at baseline will be excluded from study:

- Subjects with significant medical illness including hepatic (abnormal liver function tests), neurological, renal, cardiac, pulmonary, hematologic, gastrointestinal, or metabolic disorders.
- Subjects who are lactating, are within 6 months postpartum, or have an irregular sleep- wake cycle, e.g., from having very young children in the home.
- Subjects who are using hormonal contraception (within six months prior to the study).
- Subjects using medication that may affect outcome measures of mood, circadian rhythms or hormone levels (6-sulphatoxy-melatonin, estradiol, progesterone, FSH, LH, prolactin) within one month of initiating the study or anytime during the study. Such medications include OTC medication (excluding Tylenol), antidepressants, anti-anxiety, antihypertensive, beta blockers, and asthma medications. Vaccinations, vitamins/mineral supplements (excluding St. John's Wart, melatonin and valerian) and/or short course antibiotics will not be considered exclusionary.
- Subjects with significant psychiatric disorder (schizophrenia, bipolar disorder, anxiety disorders, eating disorders, personality disorders, sleep disorders). An ongoing major depressive episode within the last year is reason for exclusion, although a previous history of a depressive episode is not (using DSM-IV diagnostic criteria for a major depressive episode).
- Subjects with a recent history (within the past year) of drug or alcohol abuse.

- Subjects with a history of anemia, liver, kidney, cardiopulmonary, metabolic or thyroid disease within one year of participation (per patient-reported medical history).
- Subjects with irregular menstrual cycles (cycle lengths vary greater than 3 days or who fail to ovulate for 2 consecutive months).
- Subjects unlikely to cooperate with the requirements of the study.
- Subjects needing frequent or continuous use of any medication or drugs that may affect outcome measures, including alcohol (>1 drink daily) and nicotine (> 5 cigarettes daily).
- Subjects whose prospective DMR ratings do not show cyclic variation in association with the menstrual cycle (as per inclusion criteria).
- Subjects with an irregular sleep schedule, extreme chronotypes or a sleep-wake cycle that does not correspond to the environmental light-dark cycle (e.g., subjects within 2 weeks of transmeridian travel, night shift workers, or those with significant advanced or delayed sleep phase syndromes). To enhance precision of the timing of the light stimulus on circadian phase (temporal resolution), we will exclude women with habitual sleep onset times after midnight or wake times after 9 am.

4.3 Study Enrollment Procedures

Subject Selection: Before entering the study, all subjects undergo a diagnostic evaluation for 2-3 months to establish that they meet criteria for PMDD, as required by DSM-IV:

- A. In most menstrual cycles during the past year, five (or more) of the following symptoms were present for most of the time during the last week of the luteal phase, which began to remit within a few days after the onset of the menstrual flow, and were absent in the week post-menses, with at least one of the five symptoms being from among those numbered 1, 2, 3 or 4.
 1. markedly depressed mood, feelings of hopelessness, or self-deprecating thoughts
 2. marked anxiety, tension, feelings of being "keyed up" or "on edge"
 3. marked affective lability (e.g., feeling suddenly sad or tearful or increased sensitivity to rejection)
 4. persistent and marked anger or irritability or increased interpersonal conflicts
 5. decreased interest in usual activities (e.g., work, school, friends, hobbies)
 6. subjective sense of difficulty in concentrating
 7. lethargy, easy fatigability, or marked lack of energy
 8. marked change in appetite, overeating, or specific food cravings
 9. hypersomnia or insomnia
 10. a subjective sense of being overwhelmed or out of control
 11. other physical symptoms, such as breast tenderness or swelling, headaches, joint or muscle pain, a sensation of bloating, weight gain
- B. The disturbance markedly interferes with work or school or with usual social activities and relationships with others (e.g., avoidance of social activities, decreased productivity and efficiency at work or school).

- C. The disturbance is not merely an exacerbation of the symptoms of another disorder, such as major depression disorder, panic disorder, dysthymia disorder or a personality disorder (although it may be superimposed on any of these disorders.)
- D. Criteria A, B, and C must be confirmed by prospective daily ratings during at least two consecutive symptomatic cycles.

Note: Although the criteria for PMDD are in the main body of the text and formatted slightly differently in DSM-5, the diagnostic criteria for PMDD have not changed between DSM-IV and DSM-5. Thus, no alterations to the DSM-IV SCID criteria are needed to establish diagnosis.

Participants will begin the Evaluation Period at any time during their menstrual cycle. Patients will monitor their cycle days and collect ratings until two consecutive symptomatic menstrual cycles occur, per diagnostic criteria (outlined in pg.16, section 4.3). As we expect variation in menstrual cycle lengths among patients, we cannot establish a strict temporal schedule for this evaluation period. Nevertheless, we anticipate its duration to be no less than 2 (provided evaluation begins proximal to their first cycle day and they have regular, continuously symptomatic cycles) and no greater than 3 months (to allow for detection of 2 full symptomatic cycles). Scheduling the start of this evaluation period according to patients' first cycle day would increase patient burden and be prohibitive to recruitment efforts.

To facilitate understanding of study flow and design (see section 6.1), we refer to the Evaluation Period as Month 1 and Month 2 (as there are 2 full consecutive menstrual cycles within this period).

We recruit subjects through referral sources from the UCSD Dept. of Psychiatry Outpatient Services and Women's Mood Disorders Clinic, the Reproductive and Family Medicine Clinics, the Internal Medicine Group, the Student Health Service and the Counseling and Psychological Service (with all of whom the PI has a longstanding collaborative relationship -- see attached letters). Through the UCSD public affairs office, we place advertisements in local newspapers, mail flyers to local San Diego zip codes, make on-line announcements for UCSD employees/students, and place flyers or brochures at clinics, libraries and on campus bulletin boards in the San Diego area. After subjects complete an initial telephone and written screening questionnaire (Menstrual Assessment Form), we obtain a medical and psychiatric history from every subject selected for possible inclusion in the proposed study. A Clinical Rater (trained clinician) with established inter-rater reliability (kappa coefficient = 0.90) will conduct SCID⁵² interviews. During the telephone screening we will inquire on history of anemia, kidney, cardiopulmonary, metabolic, liver or thyroid disease within one year of screening. Those endorsing positive history of any of these conditions will be excluded from participation. No lab test or physical examinations are required to verify history. We will not test for existence of these medical conditions at the time of study since it would be cost prohibitive and an unreasonable burden for patients to obtain labs via outside sources, thus hindering recruitment efforts. We will obtain a urine toxicology screen and a pregnancy test. In addition, each subject will receive a thorough explanation of the study before being asked to personally sign informed written consent under supervision of the UCSD Committee on Investigations Involving Human Subjects.

During an initial 2-3 month evaluation period, subjects will complete twice-daily self ratings of mood (including core PMDD symptoms of depression, anxiety, affective lability, irritability) using a 100 mm visual analogue scale (Daily Mood Ratings form-DMR).^{54, 55} Individual items on the DMRs will be measured, scored and plotted using GraphPad Prism (GraphPad Software, Inc. La Jolla, CA) to observe the daily progression of mood symptoms (both in the morning and evening from day to day in the follicular and luteal phase) throughout the evaluation phase and in relation to the woman's menses to ensure proper diagnosis based on DSM-IV criteria. Women also will visit the clinic on a weekly basis where the project coordinator will collect the daily rating forms, and a trained clinician, blind to treatment condition, will interview the subjects using the 24-item Hamilton Rating Scale for Depression (HRSD).⁵⁶ At this time the subjects also will complete a Beck Depression and Anxiety Inventory.^{57, 58} In addition, we will ask them to complete a screening questionnaire on their sleep patterns, to keep daily sleep logs and to adhere to their habitual sleep schedule. This evaluation period will establish the diagnosis of PMDD and will provide information as to when symptoms are likely to occur. It also helps us to design a study schedule based on each patient's individual symptom patterns, and to establish each individual's sleep schedule prior to interventions. As in our previous studies and those of others,⁵⁹ we expect about 5% of patients screened to meet criteria. We especially will recruit women who are non-responsive to other interventions for PMDD, or who seek alternatives to pharmacological or chronic treatments for PMDD.

5. STUDY INTERVENTIONS

5.1 Interventions, Administration, and Duration

Treatment 1 will occur during the menstrual cycle immediately following the 2 menstrual cycles studied in the evaluation period. Washout will occur the following menstrual cycle, and Treatment 2 the menstrual cycle immediately following Washout. As we establish the Evaluation Period as Month 1 and Month 2, we will refer to Treatment 1 as occurring in Month 3, Washout in Month 4, and Treatment 2 in Month 5 (see section 6.1).

During Month 3, qualified participants will sign the Study Consent between cycle days 1 and 10, be randomized to treatment and receive all necessary instructions, forms and equipment to continue with the treatment phase. On the day of their luteinizing hormone (LH) surge (luteal phase), subjects will undergo a night of Late Wake Therapy (LWT) (sleep 21:00-01:00 h, followed by wake) vs. Early Wake Therapy (EWT) (wake until 03:00 h followed by sleep until 07:00 h) at home. We selected the specific wake and sleep times based on our previous work in PMDD.^{36, 37} The following day, subjects will receive the light intervention for 7 consecutive days: days 1-7 after the LH surge (approximately menstrual cycle days 15-21). Depending on their randomization schedule, subjects will receive, at home, 60 min of either AM bright white light (LED of 1350 lux at 20 inches) starting within 30 minutes of their habitual wake time (for those undergoing LWT), or PM bright white light ending 30 min before their habitual sleep onset time (for those undergoing EWT). The following Month 4 (Washout) will be a month of no intervention to prevent any carry-over effects from the Month 3 intervention affecting measures in Month 5. Mirroring Month 3 timing, in the luteal phase of Month 5, subjects will receive the alternate wake therapy (LWT or EWT) and light exposure (AM or PM) (see Fig. 1, above).

Sleep Interventions: Appropriate sleep and wake times during the EWT and LWT interventions will be documented by actigraphy. Compliance with wake therapy also will be monitored by having patients leave a message on an answering machine once every half-hour while awake. As they are only awake for 4 hours during wake therapy, they will make 8 calls. The potential risks of wake therapy include fatigue. Subjects will be encouraged to stay at home the day after wake therapy or, if driving, arrange alternative transportation. In previous studies of one night of total wake therapy in PMDD patients, subjects felt energized and wished to return to work or other daily activities. Previous studies also included two consecutive nights of partial wake therapy. We anticipate fewer problems in this study with only one night of partial wake therapy. Sleep and activity measures are non-invasive, but may cause some skin irritation and/or discomfort on the wrist where the Actiwatch Spectrum (Philips Respironics, Bend Oregon) is worn.

Light Interventions: Subjects will sit in front of a portable (5.5" x 6.25") Litebook® Model 1.2 light box (an array of 60 cool white light-emitting diodes behind a clear plastic screen)(The Litebook Company Ltd., Alberta Canada) with an intensity of 1,350 lux and an irradiance of 2.41×10^{-9} w/cm² at 20 in, and spectral emission peaks at 464 nm and 564 nm. Subjects will gaze at the light source for a minute every few minutes for 60 min. The distance of the subject from the light source will be calibrated individually for each light box by use of a Meterman LM631 Digital Light Meter (Meterman Test Tools, Everett, WA) to produce an intensity of 1,350 lux at 20.0 in. Ambient light intensity and spectra will be documented by the Actiwatch Spectrum. A research assistant will provide a measuring tape to ensure proper distance between light source and patient, check the Actiwatch recordings to ensure compliance, as well as the Litebook's built-in compliance monitor recordings. Since most of us are exposed to fluorescent light in our everyday lives, we do not anticipate that exposure to bright light per se will pose any special physical, psychological, social or legal risks. The intensity planned is less intense than bright sunlight, which normally exceeds 10,000-50,000 lux. Although 1,350 lux is more intense than common indoor room lighting during a 16-hour day, the average patient would receive more radiation from room lighting than from 1-2 hours of special lighting. Thus, the treatment is expected to be less hazardous than going for a walk or going to the beach. No special side effects apart from mild sleepiness (the patient needs to be awake for the light exposure and evening light may potentially disrupt sleep onset) are anticipated. It should be noted that sleep deprivation has been reported to benefit depressed patients. The possibility that the bright light treatment might potentiate a depressed patient's risk of switching into mania is recognized, although we have not seen this effect in previous studies of PMDD patients and we will exclude bipolar patients with mania from the study. If hypomania occurs, the light would be discontinued and appropriate referral and treatment with psychotropic medication, if needed, would be given.

Duration: Intervention phase will require a minimum of 3 months, provided patients have regular menstrual cycles and we can detect an LH surge (ovulation) in months 3 and 5. If a patient fails to ovulate in either month 3 or 5, she will be asked to repeat ovulation testing the following month. Two consecutive months with no ovulation will result in discontinuation of participation.

5.2 Handling of Study Interventions

After randomization, the research associate will prepare all necessary equipment and recording logs necessary for patients to complete the study. The study

coordinator and research associate, unmasked to the treatment condition, will provide the necessary instructions to ensure proper administration of treatment.

Light boxes, binders, calendars and checklists will be provided in office to facilitate patient adherence to time-specific study protocols, completion of forms, collection of required measures and at-home self-administration of the study intervention.

5.3 Concomitant Interventions

As we will study mood and endocrine effects of the intervention from baseline to post-treatment, use of hormonal contraception (within six months prior to study) and other medication (within one month prior to study) will be prohibited.

5.3.1 Allowed Interventions

Acetaminophen (Tylenol) 650 mg po every 4 hours prn pain or headache.

5.3.2 Required Interventions

N/A

5.3.3 Prohibited Interventions

Hormonal contraception (within six months prior to study) and other medication (within one month prior to study or at any time during the study) that may affect outcome measures of mood, circadian rhythms or hormone levels (6-sulphatoxy-melatonin, estradiol, progesterone, FSH, LH, prolactin) will be prohibited. Such medications include Over-the-Counter (OTC) medication (excluding Tylenol), antidepressants, anti-anxiety, antihypertensive, beta blockers, and asthma medications. Vaccinations, vitamins/mineral supplements (excluding St. John's Wart, melatonin and valerian) and/or short course antibiotics will not be considered exclusionary.

5.4 Adherence Assessment

Utilizing itemized checklists outlining each study requirement, study staff will review all data collection forms/logs on an ongoing basis for completeness and accuracy as well as compliance to study protocol. Binders, calendars and checklists will be provided to facilitate patient adherence to time-specific study protocols, completion of forms and collection of required measures. Staff will calculate adherence to protocol and continuously tabulate the results to ensure adherence to wake therapy is 100% and light is at least 85% (completing at least 6 of 7 days of light therapy). Appropriate sleep and wake times during the EWT and LWT interventions will be documented by actigraphy. Compliance with wake therapy also will be monitored by having patients leave a message on an answering machine once every half-hour while awake. As they are only awake for 4 hours during wake therapy, they will make 8 calls. To ensure compliance with light protocols, a research associate will provide a measuring tape to ensure proper distance between light source and patient, check the Actiwatch recordings during time of intervention, as well as the Litebook's built-in compliance monitor recordings.

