Using a randomized cross-over design, in the luteal phase of their menstrual cycles, PMDD women will receive either 1) one night of LWT (sleep 21:00-01:00 h, followed by wakefulness) plus 7 days of AM BWL (light-emitting diode-LED administered for 60 minutes, starting within 30 minutes of habitual wake time) or 2) EWT (wakefulness until 03:00 h, then sleep 03:00-07:00 h) plus 7 nights of PM BWL (administered 90 minutes before habitual sleep onset, for 60 minutes). Following this first intervention, patients will undergo one washout month with no intervention. The second intervention will be completed in the luteal phase of the following month and will be the treatment opposite the one previously performed. Total study duration, including evaluations and washout, will be 5 months (see Figure 1, Section 3, for detailed study flow diagram).

Sample Size and Population

In order to achieve the targeted enrollment goal of 40 completed subjects allowing for a 20% drop-out rate, 48 PMDD women ages 18-45 will be recruited to participate in the study.

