9.5 Outcomes

9.5.1 Primary Outcome

- Treatment-Related Mood Rating Changes from Baseline (month 2) to post intervention (months 3,5) :
Mood ratings include Hamilton Rating Scale for Depression (HRSD), Beck Depression Inventory (BDI), atypical depression symptoms as part of the Structured Interview Guide for the Hamilton Depression Rating Scale, Seasonal Affective Disorders version (SIGH-SAD), Beck Anxiety Inventory (BAI), mania ratings, the Psychological General Well-Being Index (PGWI) and daily mood self-ratings (DMR) that include core PMDD symptoms of anxiety and irritability as required during diagnostic evaluation, before, during and after each wake and light intervention at the same time of day (between 15:00-17:00 h). To assess more acute effects on mood that may occur more rapidly during the wake interventions, subjects will complete DMRs twice daily beginning the evening before the wake therapy intervention and continuing until the morning after the recovery night of sleep.
- Treatment-Related Urinary 6-sulfatoxymelatonin (6-SMT) Changes from Baseline (month 2) to post intervention (months 3,5) :
6-SMT is a principal melatonin metabolite that is abundant in urine, well correlated with plasma melatonin, and serves as an excellent marker for circadian phase response.
- Treatment-related changes in objective and subjective sleep measures:
Using actigraphy, we will obtain objective measures of the sleep/wake cycle to ensure appropriate sleep/wake times during wake therapy, and during the light interventions as it is an important biological rhythm with which to compare the intervention-induced melatonin rhythm changes. To assess subjective sleep quality, we will use the Pittsburgh Sleep Quality Index (PSQI) and a visual analogue scale.

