The Clinical Coordinator will instruct each patient and demonstrate procedures for completing the Urine Log and collecting, transferring urine samples to tubes (using urine kits provided to them prior to cycle day 10 in months 2, 3 and 5) and freezing samples at home. The Research Associate will telephone patients to prompt them to collect samples when menstruation approaches (based on menstruation histories), will collect frozen urine kits and data logs within 3 days of collection (but not before completion of actigraphy measures), catalogue identifying information, and store samples at -70⁰ centigrade. On the day the patient transfers samples to the laboratory, missing samples or log entries will be noted and the participant will be instructed on the importance of providing complete samples and records. As urine collections (particularly during mornings) may be problematic for women in school or work, patients that cannot collect some morning/evening urine samples are instructed to record time of missed collections in order to later extrapolate 6-SMT excretion rates before proceeding with analysis. Patients that are completely unable to collect urine will not be excluded from participation in the study as they will still collect mood, activity, light and sleep data for analysis of treatment outcomes.

Sleep Measures:

The Clinical Coordinator will instruct each patient on the proper use of the Actiwatch device and the completion of its accompanying log. Actigraphy devices and logs will be collected by the research associate at the same time as the urine samples. Data will be verified against logs to ensure completeness and accuracy, as well as to monitor compliance with sleep and light protocols. Compliance with wake therapy will be monitored by means of half-hourly message left to a laboratory voice mail. Timing of these messages must correspond to the required treatment time. Failure to comply with wake therapy will result in repetition of wake therapy prior to commencing light treatment.

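### The wake-therapy check assumes 4 hours awake and 8 calls in both arms, but LWT wakefulness is open-ended from 01:00, so the calls may stop before the required interval does

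*Combined protocol and SAP*

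**What the plan says.** **The check.** Sections 3, 5.1 and 5.4 describe compliance monitoring for the wake-therapy night in the same terms and without distinguishing the arms. Actigraphy documents sleep and wake times, and compliance is also monitored by "having patients leave a message on an answering machine once every half-hour while awake". The next sentence fixes the count: "As they are only awake for 4 hours during wake therapy, they will make 8 calls".

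**The schedules.** The Précis defines LWT as "one night of LWT (sleep 21:00-01:00 h, followed by wakefulness" and EWT as "EWT (wakefulness until 03:00 h, then sleep 03:00-07:00 h". Sections 3, 5.1, 6.2.2 (Randomization) and 9.2 (Treatment Assignment Procedures) give the same clock times. None gives an end for LWT wakefulness, a return to sleep that night, or a start for the EWT wake period. Section 9.5.1 places the next sleep later: twice-daily mood ratings run from the evening before wake therapy, "continuing until the morning after the recovery night of sleep".

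**The consequence of failing.** Section 5.4 sets the wake-therapy adherence target at 100%. Section 10.3.3 says of the voicemails: "Timing of these messages must correspond to the required treatment time". It also requires wake therapy to be repeated before light treatment if the participant did not comply.

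**Eligible sleep times.** Section 4.2 states: "we will exclude women with habitual sleep onset times after midnight or wake times after 9 am".

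**The concern.** A single figure of 4 hours is applied to two arms whose wake periods are set differently. One arm starts at 01:00 and is open-ended; the other ends at 03:00 and has no stated start. For LWT the figure also sits badly with the sentence before it, because a woman who stays awake past 05:00 and calls every half-hour makes more than 8 calls.

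If staff count to 8, a woman in LWT could make every call, go back to sleep after about 05:00 and be passed as compliant. The unchecked hours would be the end of the late-night wake period, in the arm hypothesised to be superior. Undetected sleep there would weaken the contrast under test. Separately, a 100% target cannot be calculated consistently while the interval it refers to is undefined.

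**Working it through.** **Inputs from the documents.** One call per half-hour, so 2 per hour; 4 h and 8 calls (Sections 3, 5.1, 5.4). LWT wake from 01:00; EWT wake until 03:00 (Précis and four later sections). Latest eligible habitual wake time 09:00 and latest habitual sleep onset 24:00 (Section 4.2).

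**Assumptions.** The LWT end times and EWT start times below, because the plan states none. The 07:00 LWT end borrows the EWT rise time. The 09:00 end is an eligibility limit, not a treatment time.

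**Step 1: the plan's figure.** Calls = hours awake × 2. So 4 × 2 = 8, which reproduces exactly. The multiplication is right; the question is the 4 h.

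**Step 2: where 8 calls end in LWT.** 8 ÷ 2 = 4 h, and 01:00 + 4 h = 05:00.

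**Step 3: LWT by assumed end.** Hours = end − 01:00; calls = hours × 2; share covered = 4 ÷ hours.

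| Assumed end | Hours | Calls needed | Covered by 8 calls | Hours not covered |
|---|---|---|---|---|
| 05:00 | 4 | 8 | 100% | 0 |
| 06:00 | 5 | 10 | 80% | 1 |
| 07:00 | 6 | 12 | 67% | 2 |
| 09:00 | 8 | 16 | 50% | 4 |

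The gap is zero only if LWT wakefulness is required no later than 05:00.

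**Step 4: EWT by assumed start.** Hours = 27:00 − start (27:00 being 03:00 the next day).

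| Assumed start | Hours | Calls needed |
|---|---|---|
| 24:00 | 3 | 6 |
| 23:00 | 4 | 8 |
| 22:00 | 5 | 10 |
| 21:00 | 6 | 12 |

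Four hours fits EWT only for a 23:00 start. From 22:00, 8 calls cover 8/10 = 80%; from 21:00, 8/12 = 67%.

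**Step 5: which check is available in time.** Wake therapy is on the night of the LH surge and light starts on LHS+1 (Appendix I). Section 10.3.3 says watches are collected together with the urine samples, and Appendix I has equipment returned at LHS+11. A repeat of wake therapy must come before light starts. Of the two wake checks, only the voicemails are therefore scheduled in time to trigger it.

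**The case against.** The strongest reply is that no LWT window longer than 4 hours is actually printed. A reader might infer from the eligibility limits that the plan states a wake period of 5 to 8 h. It does not: it states a start and no end. That objection stands, and every figure in Step 3 beyond the 05:00 row depends on an assumed end.

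Second, the half-hourly rule, together with the requirement that message times match the treatment time, may already demand calls after 05:00, with 8 merely a consequence drawn from it. On that reading there is no gap. But the text states both the rule and the count and does not say which governs.

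Third, actigraphy runs from the day of the LH surge, so sleep after 05:00 would be recorded. This also stands: a reader might conclude that such sleep would go undetected, and the documents do not support that. The limitation is timing (Step 5). Section 5.4 has recordings checked for the time of the intervention, but that sentence concerns the light protocol, and no watch download before LHS+11 is scheduled. The plan also gives no numerical actigraphy criterion for wake therapy.

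Fourth, a reader might infer that EWT is almost fully verified and LWT is not. Step 4 shows why that goes too far: EWT coverage can also be 80% or 67%, overlapping the LWT range.

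Finally, nothing in the documents says how many women would return to sleep. Less complete LWT delivery would more plausibly shrink the hypothesised LWT advantage than create a false one.

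**Conclusion.** The inconsistency is real and worth correcting. The 4-hour, 8-call statement conflicts with LWT wakefulness that is open-ended from 01:00, and with the rule of one call every half-hour while awake. If the count of 8 governs, the LWT call check ends at about 05:00. It then covers 80%, 67% or 50% of the added wake period for assumed ends of 06:00, 07:00 or 09:00, leaving 1, 2 or 4 h outside it. There is no gap if the period ends by 05:00.

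Four hours is not assured in EWT either (3 to 6 h for starts from 24:00 to 21:00). A difference in coverage between the arms is therefore likely, not certain. The gap concerns the call check only; actigraphy would still show later sleep, but after the point at which a repeat could be ordered. No effect on an outcome can be sized from the documents.

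**What to change.** 1. Reconcile the 4-hour, 8-call statement (Sections 3, 5.1, 5.4) with the LWT and EWT schedules (Précis, Sections 3, 5.1, 6.2.2, 9.2) and with the message-timing and repeat rules in Section 10.3.3.
2. Have the sponsor state the start and end of the required wake interval in each arm. No sleep or wake schedule is proposed here.
3. Make the half-hourly calls span that whole interval, with the count following from its length and set per arm if the lengths differ.
4. Assess the 100% wake-therapy adherence target by actigraphy over the same interval in both arms, and write down the criterion used, since none is given now.

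The cost is a text correction and a few extra voicemails on one night; on the assumed LWT ends of 06:00 to 09:00, that is 2 to 8 more calls (10 − 8 to 16 − 8).
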